11.0 ADVERSE EVENT REPORTING

11.1 Definitions

Adverse events: Any untoward medical occurrence in a human subject, including any abnormal sign (e.g., abnormal physical exam or laboratory finding), symptom, or disease, temporally associated with the subject's participation in the research, whether or not considered related to the subject's participation in the research.

This will include:

- Expected events related to the subject's disease process during active enrollment in the research protocol and do not directly result from use of the investigational device or study.
- Procedural events directly related to the cardiac catheterization procedure and recovery from the procedure and do not directly result from use of the investigational device.

Serious Adverse Event (SAE): A serious adverse event that results in any of the following and NOT directly related to the device. This includes any event that

- Results in death
- Is life-threatening (places the subject at immediate risk of death from the event as it occurs);
- results in in-patient hospitalization or prolongation of existing hospitalization;
- results in a persistent or significant incapacity;
- results in a congenital anomaly/birth defect (not relevant to this study); or
- based upon appropriate medical judgment, may jeopardize the subject's health and may require medical or surgical intervention to prevent one of the other outcomes listed in this definition.

Adverse Device Effect (ADE): Any untoward or unintended response to a medical device. This definition includes any event resulting from insufficiencies or inadequacies in the instructions for use or the deployment of the device or any event that is a result of user error.

During this clinical investigation an event should be considered related to the device when it is the result of:

- LAMPOON procedure
- Edwards Sapien 3 transcatheter heart valve or accessories
- Asahi-Intecc Astato XS 20 guidewire

An event will be considered NOT related to the LAMPOON procedure when it is the result of:

- A pre-existing medical condition
- Clearly attributable to TMVR but not LAMPOON part of procedure (example: commissural paravalvular leak)

Anticipated Adverse Device Effects (AADEs): An AADE is an adverse event with a reasonable possibility that the device or procedure caused or contributed to the event. The following AADEs are considered anticipated based on previous human experience:

- LAMPOON device failure including failure to traverse, to lacerate, or to position catheters or guidewires
- Valve malposition, reposition, dislocation, migration, or embolization or deployment in unintended location
- Interatrial shunt

- LVOT gradient
- Aortic valve injury
- Paravalvular leak
- Atrial-ventricular conduction defects to include bundle branch block and complete heart block requiring placement of a temporary or permanent pacemaker
- Cardiac arrhythmia including ventricular tachycardia and atrial fibrillation
- Transient myocardial dysfunction attributed to rapid ventricular pacing required for mitral valve implantation, including brady-asystole or pulseless electrical activity, or requiring cardiopulmonary resuscitation
- Angina and myocardial ischemia
- Coronary artery obstruction or injury that may require intervention
- Myocardial infarction
- Congestive heart failure or BNP elevation
- Cardiogenic shock that may require intervention
- Infective endocarditis
- Left ventricular or left atrial perforation
- Pericardial effusion or tamponade
- Hypertension
- Hypotension requiring vasopressor support or mechanical circulatory support
- Stroke or TIA or seizure
- Hemolysis which requires transfusions and which requires confirmatory dramatic schizocytes and haptoglobin decline
- Low platelets or thrombocytopenia or increased or reduced leukocytes
- Mechanical injury to the myocardium, access vasculature, cardiac valves that may require intervention or that may elevate Troponin
- Bleeding causing anemia and blood transfusions
- Mitral valve thrombosis
- Embolization of air, calcific valve material, atheroma, or thrombus to coronaries, brain, limbs, or viscera causing myocardial infarction, stroke, or limb ischemia
- Retroperitoneal bleed or hematoma or access site injury
- Contrast-induced nephropathy requiring temporary or permanent hemodialysis or medical treatment
- Volume overload, pleural effusion, or dyspnea from procedure-related volume perturbations
- Respiratory failure requiring oxygen or mechanical support or mechanical ventilation
- Infection including access site or urinary or pulmonary or including sepsis
- Pain including back pain and access site and generalized
- Cardiac arrest
- Death

Serious Adverse Device Effect (SADE): An adverse effect that may have been or is attributed to the use of the device and produce an injury or illness that is life-threatening, results in permanent impairment or damage to the body, or requires medical or surgical intervention to prevent permanent harm to the body.

Unanticipated Adverse Device Effect (UADE): Any serious adverse effect on health or safety or any life-threatening problem or death caused by, or associated with, a device, if that effect, problem, or death was not previously identified in nature, severity, or degree of incidence in the investigational plan or application (including a supplementary plan or application), or any other unanticipated serious problem associated with a device that relates to the rights, safety, or welfare of subjects (21 CFR 812.3(s)).

Unanticipated Problem (Up): An unanticipated problem is any incident, experience, or outcome that meets ALL of the following criteria:

- Unexpected in terms of nature, severity, or frequency in relation to:
- a. the research risks that are described in the IRB-approved research protocol and informed consent document, Investigator's Brochure or other study documents, and
- b. the characteristics of the subject population being studied, and
 - Related or possibly related to participation in the research, and
 - Places subjects or others at a greater risk of harm (including physical, psychological, economic, or social harm) than was previously known or recognized.

Protocol Deviation: A protocol deviation is any change, divergence, or departure from the study design or procedures of an IRB-approved research protocol.

11.2 Adverse event management:

The following adverse event management guidelines are intended to ensure the safety of each subject while on the study. Adverse events and adverse device effects will be attributed to study procedure and graded by severity according to the following tables:

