11.2.3 Adverse Event Reporting

Adverse event recording will start on Day (0) of the LAMPOON TMVR procedure and will continue through the 12-month Follow Up. New events or conditions present at baseline that increase in severity will be recorded and evaluated and reported on the case report form. Once the subject has completed the 30-day follow up, only serious adverse events (SAE), serious adverse device effects (SADE), unanticipated device effects (UADE) and unanticipated problems (UP) will be reported to the Sponsor. It is the responsibility of the site investigator to report adverse events and adverse device effects to their respective IRBs or other regulatory bodies according to their reporting requirements. Monitoring visits will be conducted by the Sponsor to review source documentation, and accuracy and completion of the adverse event case report forms.

11.2.4 Adverse event reporting timeframes:

Serious Adverse Events (SAEs)

- All serious adverse events will be reported to the Sponsor immediately but not later than 3
 working days from the event. The respective institutional IRB should be notified according to
 their requirements.
- The serious adverse event will be evaluated by the sponsor. If determined to be an unanticipated adverse device effect that increases the risk to the participating subjects, the sponsor will terminate the investigation within 5 days after making the determination, and not later than 15 working days after the sponsor was first notified of the event. [21 CFR 812.46]

Unanticipated Adverse Device Effects (UADE)

- Must be reported to the Sponsor and the institutional IRB immediately but no later than 10 working days after the investigator learns of the event. [21 CFR 812.150]
- Unanticipated Adverse Device Effects should be reported via telephone as well as on the adverse event section of the case report form.
- If the event is determined by the Sponsor to be a UADE, the Sponsor will report the event to all investigators to enable reporting to their respective IRB/regulatory bodies. The Sponsor will provide this notification to participating sites and to the FDA within 10 working days after they first receive notice of the effect. [21 CFR 812.150]

 All Unanticipated Adverse Device Effects will be reported by the Sponsor to the NIH IRB per NIH Policy 801 "Reporting Research Events".

Deaths

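### After the 30-day visit, an anticipated, directly device-related admission that is serious only because of hospitalization is not reportable to the sponsor, while the same admission from an unrelated illness is

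*Combined protocol and SAP*

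**What the plan says.** Section 11.1 sets two seriousness standards, divided by relation to the device.

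- **SAE.** The definition opens "A serious adverse event that results in any of the following and NOT directly related to the device". Its criteria include an event that "results in in-patient hospitalization or prolongation of existing hospitalization", and also persistent or significant incapacity.
- **Device-related.** In this study "an event should be considered related to the device when it is the result of" the LAMPOON procedure, the "Edwards Sapien 3 transcatheter heart valve or accessories", or the Astato guidewire.
- **SADE.** The criteria are "injury or illness that is life-threatening, results in permanent impairment or damage to the body, or requires medical or surgical intervention". The intervention limb counts only where its purpose is to avert lasting harm. Neither hospitalization nor non-permanent incapacity appears.
- **UADE and UP.** Both are reserved for what was not foreseen: a UADE must be unanticipated, and a UP must be unexpected.

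Section 11.2.3 then narrows what sites send. After the 30-day visit, "only serious adverse events (SAE), serious adverse device effects (SADE), unanticipated device effects (UADE) and unanticipated problems (UP) will be reported to the Sponsor". Adverse event recording itself runs from the procedure to 12 months.

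**The concern.** The four reportable categories should together catch every serious event, whatever its cause. They do not, because the criterion that most often makes a late event serious without its being dangerous, namely admission to hospital, sits only in the definition that excludes direct device effects. From the 30-day visit to 12 months, an admission for an unrelated illness goes to the sponsor as an SAE. An admission with the same course, caused by the valve or the laceration, need not go at all.

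That asymmetry favors the test article in any tally of serious events built from sponsor reports over this period. The protocol summary (section 1.0) places 12-month outcomes in the secondary analysis, and section 4.0 names late valve thrombosis as a reason for follow-up imaging, so late device effects are of interest to this study.

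**Working it through.** The plan states no figure on this point, and the check is one of logic. Take an admission after the 30-day visit that is a direct result of LAMPOON, the valve or the guidewire, is of a kind already on the anticipated list, is not life-threatening, leaves no permanent impairment or damage, and needs no intervention to prevent permanent harm. Test it against each category that section 11.2.3 keeps.

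1. **SAE.** The hospitalization criterion is met, but the definition's opening clause removes events directly related to the device. Not an SAE.
2. **SADE.** There are three limbs: life-threatening, permanent impairment or damage, and intervention to prevent permanent harm. By construction none is met, and admission alone is not a limb. Not a SADE.
3. **UADE.** This requires an effect, or some other serious device problem, that was not anticipated. The list in section 11.1 already names heart failure, paravalvular leak, hemolysis, mitral valve thrombosis, arrhythmia, infection and volume overload. Not a UADE, unless its severity or incidence goes beyond what was foreseen.
4. **UP.** This requires the event to be unexpected. Not a UP, for the same reason.

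Now change only the cause to an unrelated illness. Step 1 reverses: the admission is an SAE, which section 11.2.4 requires within 3 working days.

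Two details bear on whether the case is realistic.

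- Section 11.1 says an event clearly due to TMVR rather than LAMPOON is not LAMPOON-related, with commissural paravalvular leak as the example. That does not return the event to the SAE definition, because the valve is itself listed as a device.
- Appendix A gives the impact of paravalvular leak as left ventricular failure, with severity 2 and score 6. The likelihood character did not survive extraction, but 6 / 2 = 3, which the key calls common. Severity 2 is described as hard to correct but without expected harm to the patient. A site applying that rating could reasonably decide that a short heart-failure admission from a leak did not involve preventing permanent harm.

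On size, the documents support only a number at risk. If all 30 subjects are treated, nobody withdraws, and 30-day mortality lies between the two anticipated rates in section 10.3 (10% and 30%), then 30 x 0.70 = 21 to 30 x 0.90 = 27 subjects reach the restricted-reporting period. Two further rates are needed: the proportion with a device-related admission by 12 months, and the fraction of those admissions that are anticipated and serious only through hospitalization. The documents give neither.

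**The case against.** The case on the other side has several parts.

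**Many device-related admissions are still reportable.** A reader might infer that every valve- or LAMPOON-related admission after 30 days escapes reporting. The documents do not support that. An admission that is life-threatening, leaves permanent damage, or needs intervention to prevent permanent harm is a SADE, and the SADE wording on attribution is broad. An unanticipated one can be a UADE or UP. One only indirectly related to the device is not clearly excluded from the SAE definition. Hemolysis is a poor example, since section 11.1 lists it as anticipated when transfusion is needed, and transfusion may well satisfy the intervention limb. All of this stands, and it is why the point is confined to the residual case.

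**The data are not lost.** Events are recorded on the case report form to 12 months, and sponsor monitoring visits review those forms against source. Hemolytic anemia, paravalvular leak, device thrombosis and TMVR-related infection are exploratory endpoints in section 10.2.3. The 6- and 12-month visits collect echocardiography, blood tests and an adverse event assessment. This also stands, but recording an event does not make it reportable or count it as serious. The other safeguards do not reach it: section 10.2.5 adjudicates deaths, primary endpoints, valve embolization and site-reported strokes, and the IRB review described in section 10.3 covers SAEs, UADEs and UPs.

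**The safety objective is at 30 days.** Section 1.0 defines it as freedom from MACE to discharge and 30 days, and the reporting restriction starts only afterwards. A reader might infer that the primary safety result is biased; it is not.

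**The root is the SAE exclusion.** Deleting that clause would close the gap without touching the SADE text. That is correct, and it offers a second route to the fix. It does not show that the gap is absent.

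**Conclusion.** The gap is real and narrow. An anticipated, directly device-related admission that is serious only because of hospitalization meets none of the four categories reportable to the sponsor after the 30-day visit, while its unrelated counterpart is a reportable SAE. The consequence is incomplete sponsor reporting, and a serious-event tally between 30 days and 12 months that leans toward the device.

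The number of affected admissions cannot be derived. A reader might assume that 10% to 30% of the 21 to 27 subjects have a device-related admission, giving 21 x 0.10 = 2.1 to 27 x 0.30 = 8.1, and call these the missing reports. The documents support neither that rate nor the step from all device-related admissions to unreported ones. Even under the assumed rates this range is a ceiling, and the true count could be near zero.

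The conclusion assumes that sites apply the definitions as written. Section 11.2.4 suggests that some might not: it has the sponsor assess whether a reported SAE is an unanticipated device effect, which presumes that an SAE can be device-related, contrary to section 11.1. That inconsistency is a further reason to correct the text. Label: wrong as written.

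**What to change.** Use one set of seriousness criteria for related and unrelated events. Either of two edits to section 11.1 closes the gap:

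- add in-patient or prolonged hospitalization, and persistent or significant incapacity, to the SADE criteria; or
- delete the clause that limits SAEs to events not directly related to the device.

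The edits are equivalent in making the admission reportable after 30 days, but differ in what follows. Section 11.2.4 gives a timeframe for SAEs, UADEs and deaths but none for SADEs, and the IRB review in section 10.3 does not name SADEs. Under the second edit the admission takes on the 3-working-day limit and the IRB review; under the first, those would need separate wording. Whichever is chosen, bring sections 11.2.3 and 11.2.4 into line with it, so that the sponsor's assessment of an SAE as a possible device effect agrees with the definition.

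The cost is a line or two of text and a few more site reports between 30 days and 12 months. No visit, test or endpoint changes.

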11.2.1 Grading of adverse events and adverse device effects

Category	Description
Mild	Awareness of symptom. Not expected to have a clinically significant effect on the subject's condition. Not surpassing the expected standard medical intervention.
Moderate	Condition creates a level of discomfort that interferes with the subject's usual activity or affects clinical status. May require medical intervention.
Severe	Incapacitating and significantly affects the subject's clinical status. Likely requires medical intervention and prolonged hospitalization.

11.2.2 Attribution of adverse events to the research protocol

The relatedness of adverse events will be classified as:

Description
The event is clearly related to the research protocol.
The event is likely related to the research protocol. The event has a reasonable temporal relationship to the research device or research procedure and alternative causes, such as underlying disease, concomitant medications, or concomitant treatment-can be excluded.
The event may be related to the research protocol. The event has a reasonable temporal relationship to the research device or research procedure, and

	attribution of the event to the device or procedure cannot be excluded. However, alternative causes—such as underlying disease, concomitant medications, or concomitant treatments—are presumably responsible.
Unlikely	It is doubtful the event is related to the research protocol. The event can reasonably be explained by other factures, including underlying disease, concomitant medications, or concomitant treatments.
Unrelated	The event is clearly not related to the research protocol. There either is no temporal association with the research device or procedure, or the event is readily explained by other factures, including underlying disease, concomitant medications, or concomitant treatments.

11.2.3 Adverse Event Reporting

Adverse event recording will start on Day (0) of the LAMPOON TMVR procedure and will continue through the 12-month Follow Up. New events or conditions present at baseline that increase in severity will be recorded and evaluated and reported on the case report form. Once the subject has completed the 30-day follow up, only serious adverse events (SAE), serious adverse device effects (SADE), unanticipated device effects (UADE) and unanticipated problems (UP) will be reported to the Sponsor. It is the responsibility of the site investigator to report adverse events and adverse device effects to their respective IRBs or other regulatory bodies according to their reporting requirements. Monitoring visits will be conducted by the Sponsor to review source documentation, and accuracy and completion of the adverse event case report forms.

11.2.4 Adverse event reporting timeframes:

Serious Adverse Events (SAEs)

- All serious adverse events will be reported to the Sponsor immediately but not later than 3
 working days from the event. The respective institutional IRB should be notified according to
 their requirements.
- The serious adverse event will be evaluated by the sponsor. If determined to be an unanticipated adverse device effect that increases the risk to the participating subjects, the sponsor will terminate the investigation within 5 days after making the determination, and not later than 15 working days after the sponsor was first notified of the event. [21 CFR 812.46]

Unanticipated Adverse Device Effects (UADE)

- Must be reported to the Sponsor and the institutional IRB immediately but no later than 10 working days after the investigator learns of the event. [21 CFR 812.150]
- Unanticipated Adverse Device Effects should be reported via telephone as well as on the adverse event section of the case report form.
- If the event is determined by the Sponsor to be a UADE, the Sponsor will report the event to all investigators to enable reporting to their respective IRB/regulatory bodies. The Sponsor will provide this notification to participating sites and to the FDA within 10 working days after they first receive notice of the effect. [21 CFR 812.150]

 All Unanticipated Adverse Device Effects will be reported by the Sponsor to the NIH IRB per NIH Policy 801 "Reporting Research Events".

Deaths

- The investigator will notify the Sponsor immediately but within 3 working days of notification of a subject's death, whether the death is device related or clinical condition. Institutional IRB's will be notified according to the specific institutional regulatory requirements for reporting a death.
- The Sponsor will notify the NIH IRB of a subject's death, if applicable, per NIH Policy 801 "Reporting Research Events".
- A subject's death will be recorded on the Case Report Form.

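### For a non-fatal serious device effect, Sections 11.1 and 11.2.4 leave two site-to-Sponsor limits, 3 or 10 working days, and the literal definitions select the longer one

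*Combined protocol and SAP*

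**What the plan says.** Section 11.1 defines an SAE as "A serious adverse event that results in any of the following and NOT directly related to the device". The same section counts an event as device related when it results from the LAMPOON procedure, the Sapien 3 valve or the Astato guidewire. A UADE is "Any serious adverse effect on health or safety or any life-threatening problem or death caused by, or associated with, a device", provided that it was not previously identified in the investigational plan.

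Section 11.2.4 then sets the limits for sites:

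- **SAEs:** "All serious adverse events will be reported to the Sponsor immediately but not later than 3" working days, counted from the event. The Sponsor evaluates each one: "If determined to be an unanticipated adverse device effect that increases the risk to the participating subjects, the sponsor will terminate the investigation". It then has 5 days from that determination, and must act "not later than 15 working days after the sponsor was first notified of the event".
- **UADEs:** "Must be reported to the Sponsor and the institutional IRB immediately but no later than 10 working days after the investigator learns" of it. Telephone reporting is requested as well as the case report form.
- **Deaths:** "immediately but within 3 working days of notification of a subject's death, whether the death is device related or clinical condition".

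Section 11.2.3 lists serious adverse device effects (SADEs) among the events still reportable to the Sponsor after the 30-day visit. Section 11.2.4 gives them no limit of their own.

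**The concern.** Apply the definitions as written to a non-fatal, serious, unexpected injury caused by the laceration. It is device related, so under 11.1 it is not an SAE. It is a UADE, and the site has 10 working days. A serious event with no connection to the device has 3. The event that says most about the technique under test thus has the looser limit. The SAE block of 11.2.4 points the other way, because it speaks of all serious events and has the Sponsor pick UADEs out of them. Two sites could treat the same event differently and both be compliant.

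At stake is how soon the Sponsor, and through it up to 8 sites, hears of an unexpected device harm. The Sponsor's own 10 working days to inform the other sites start only when it receives notice, so any delay at the site is added to that.

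The starting points also differ. The SAE clock runs from the event, while the other two run from when the investigator learns of the event or is notified of the death. An SAE treated at another hospital and first heard of at a follow-up visit can be overdue before the site could have reported it.

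**Working it through.** The protocol gives no figure of its own to reproduce. The check sets the rules side by side and then sizes the gap.

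**1. The limits**

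| Category | Scope in Section 11.1 | Outer limit to Sponsor in 11.2.4 | Clock starts |
|---|---|---|---|
| SAE | serious, not directly device related | 3 working days | the event |
| UADE | serious, device associated, not previously identified | 10 working days | investigator learns |
| Death | any cause, device related or not | 3 working days | notification |
| SADE that is anticipated | serious, attributed to the device | none stated | none stated |

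**2. One test event: non-fatal, serious, unexpected, caused by the device**

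- By the definitions in 11.1: not an SAE, so the UADE limit applies, 10 working days.
- By the SAE block of 11.2.4: a serious event, so 3 working days, after which the Sponsor decides whether it is a UADE.
- Gap, with both limits counted from the day the investigator learns: 10 − 3 = 7 working days. This is a ceiling, since a site may report sooner.
- If the same event is fatal, the death rule gives 3 working days and the gap disappears.

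**3. The gap in subjects treated**

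Assumption: about 21.7 working days per month (52 × 5 / 12), so 7 working days = 7 / 21.7 = 0.32 months.

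- Pace in Section 8.0: 9 patients in about 5 months at two centers = 1.8 per month (0.9 per center-month). 1.8 × 0.32 = about 0.6 subjects.
- Pace implied by the Protocol Summary: a six-year study less five years of participation leaves about one year of enrollment, if that reading is right. 30 / 12 = 2.5 per month. 2.5 × 0.32 = about 0.8 subjects.

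**4. Time until the other sites are told**

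With the Sponsor's 10 working days added, the outer limit is 10 + 10 = 20 working days on the UADE route. It would be 3 + 10 = 13 with a 3-day site limit. The difference is the same 7 days.

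**5. The SAE clock**

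If a site learns of an SAE d working days after it happened, it has 3 − d working days left. For d greater than 3 this is negative. Adverse event recording runs to the 12-month visit, and the scheduled visits after 30 days are at 6 and 12 months, so d can far exceed 3 for an event treated elsewhere.

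**The case against.** Four arguments on the other side carry weight.

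- The protocol attributes the 10 working days to 21 CFR 812.150, and a stricter limit is the sponsor's choice. This stands as regards compliance. It does not explain which limit a site should follow when two apply.
- All three rules ask for immediate reporting, and UADEs are also to be telephoned. This stands: the limits are outer bounds and not expected delays, so the subject counts above are ceilings as well.
- The SAE block already sends all serious events to the Sponsor within 3 working days, so the UADE limit may seldom govern. That is a fair reading of 11.2.4, but it requires setting aside the SAE definition in 11.1. The sections need reconciling.
- The class is narrow. Section 11.1 lists many serious device harms as anticipated, including perforation, tamponade, stroke and cardiac arrest. This stands, and it means that both the problem and the burden of the fix are small. Those anticipated harms are SADEs when serious, however, and 11.2.4 sets no limit for them.

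A reader might also infer more than the documents support:

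- **That the events able to end the trial reach the Sponsor last.** Section 10.3 names deaths as well as serious UADEs as grounds for termination, and the stopping boundaries in 10.3.1 and 10.3.2 count only 30-day deaths. Deaths carry the 3-day limit even when device related.
- **That labelling an event a UADE moves the outer limit for termination from 3 + 15 = 18 to 10 + 15 = 25 working days.** The 18 runs from the event and the 25 from the investigator learning of it, so they cannot be compared directly.
- **That the Section 8.0 pace holds at all 8 sites.** That would be 0.9 × 8 = 7.2 subjects per month and would fill 30 places in 30 / 7.2 = about 4 months, which does not fit the roughly one year implied by the stated durations.

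**Conclusion.** The point holds for non-fatal serious device effects only. Sections 11.1 and 11.2.4 give conflicting site-to-Sponsor limits for the same event, and the literal definitions lead to the longer one. The permitted gap is up to 7 working days, or about 0.6 subjects at the two-center pace and about 0.8 if 30 subjects enroll over one year. Both counts assume that the site waits until the last permitted day and that enrollment is steady. Two related gaps also stand: the SAE clock can run out before the site knows of the event, and anticipated SADEs have no stated limit. None of this affects an endpoint or a stopping boundary. It is an inexpensive improvement to safety reporting and does not show that the protocol breaches the rule it cites.

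**What to change.** In Section 11.2.4, require sites to report every serious event (SAE, SADE, UADE or suspected UADE), whether or not device related, to the Sponsor within 3 working days after the investigator learns of it. Keep 10 working days as the outer limit for UADE reports to the IRB and FDA. In Section 11.1, reconcile the wording that excludes device-related events from the SAE definition with the SAE block of 11.2.4, so that each event falls under one rule.

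This gives serious events one limit to the Sponsor and one starting rule, covers SADEs, and removes the clock that can expire unseen. It does not by itself speed notice to the DSMB, because Section 10.3 ties UADE submissions to the IRB timeline.

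The cost is a few sentences in an amendment and a tighter limit for a small number of events. Sites already report SAEs and deaths on a 3-working-day limit.
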